16.2 Attribution to study treatment

Assessment of the relationship or relatedness of an AE to study treatment (cabozantinib, pembrolizumab) or protocol procedure will be performed by the investigator who is a qualified physician, using the respective Investigator’s Brochures as a references. Relevant factors for this determination include exposure history, temporal relationship, reaction to de-challenge or re-challenge, and confounding factors such as concomitant medication, concomitant diseases, and relevant history.

The relationship to study treatment or procedure will be described by the following: *definite, probable, possible, unlikely, or unrelated*. For simplification of reporting, AEs may be grouped as:

- **Not Related (unlikely, unrelated):** an AE that is not associated with the study treatment and is attributable to another cause or there is no evidence to support a causal relationship;
- **Related (definite, probable, possible):** an AE where a causal relationship between the event and the study treatment is a reasonable possibility. A reasonable causal relationship is meant to convey that there are facts (e.g. evidence such as de-challenge/re-challenge) or other clinical arguments to suggest a causal relationship.

Attribution to study drugs for abnormal liver function lab tests should be considered carefully in the context of oncology patients. There should be no evidence of biliary obstruction, such as elevated alkaline phosphatase, progression of malignancy, or other explanation (viral hepatitis, other hepatotoxic drugs).

16.3 Parameters of assessment for AEs and SAEs

AEs and SAEs must be assessed by the treating investigator and recorded based on the following parameters.

Parameter	Description	
CTCAE v5 grade	Grade 1	Mild; asymptomatic or mild symptoms; clinical or diagnostic observations only; intervention not indicated.
	Grade 2	Moderate; minimal, local or non-invasive intervention indicated; limiting age-appropriate instrumental ADL.
	Grade 3	Severe or medically significant but not immediately life-threatening; hospitalization or prolongation of hospitalization indicated; disabling; limiting self-care ADL.
	Grade 4	Life threatening consequences; urgent intervention indicated.
	Grade 5	Death related to AE
Seriousness	Does AE meet the definition of an SAE? (see Section 16.1 for definition)	
Duration	Record the start and stop dates of the adverse event or ongoing. If less than 1 day, indicate the length of time.	
Action taken	Did the AE cause each of the study drugs to be: held, dose reduced, discontinued, no action taken?	
Relationship to study drug(s)	What is the relationship of the AE to each of the study drug: unrelated, unlikely related, possibly related, probably related, definitely related? (see Section 16.2)	
Treatment required	Was treatment required for the AE (e.g. antibiotic, supportive medication)?	
Outcome	Is AE: ongoing, improved, stable, worsened, resolved?	

16.4 Monitoring and recording AEs

16.4.1 Responsibility for adverse event monitoring

Investigators (principal investigator, sub-investigators) and appropriately qualified clinical research staff will review participants' treatment activity, clinical status, and safety information/AEs on an ongoing basis.

16.4.2 Time frame for AE monitoring

AEs will be monitored from the time of informed consent through 30 days following the final dose of cabozantinib or pembrolizumab (whichever is later). AEs with an onset date prior to informed consent will be recorded only in the case of worsening of the AE during study participation. All AEs will be followed until resolution, return to baseline, or deemed clinically insignificant by the treating investigator, even if they occur after treatment discontinuation for up to 30 days (or until the patient starts subsequent anticancer therapy, whichever is earliest).

SAEs of any cause will be monitored from the time of informed consent through 30 days and SAEs attributed to study procedure or treatment occurring more than 30 days after treatment discontinuation must be followed until either resolution, return to baseline, or determination by the investigator that the event has become stable or irreversible.

All pregnancies and exposure during breastfeeding will be monitored and reported from the time of treatment initiation through 120 days following cessation of study treatment, or 30 days following cessation of study treatment if the participant initiates new anticancer therapy must be reported by the investigator. If pregnancy or lactation exposure occurs, the site must also contact the subject at least monthly and document the participant's status until the pregnancy has been completed or terminated.

Additionally, any SAE brought to the attention of an investigator at any time outside of the time period specified above must be reported immediately by the investigator if the event is considered to be drug-related.

16.4.3 Laboratory data

All laboratory data required by this protocol and any other clinical investigations should be reviewed. Any abnormal value that leads to a change in subject management (e.g. dose reduction or delay or requirement for additional medication or monitoring) or that is considered to be of clinical significance by the investigator should be reported as an AE or SAE as appropriate.

16.4.4 Recording AEs

All AEs, serious and non-serious, will be recorded in study-specific CRF forms. AE terms recorded on the CRF will be mapped to preferred terms using the Medical Dictionary for Regulatory Activities (MedDRA). For each AE, the investigator will provide the onset date, end date, severity grade (defined by NCI CTCAE v5), seriousness, action taken with the study drug(s), treatment required, and outcome (see Section 16.3). The list of medications administered for the treatment of the AEs will be recorded.

The investigator's signed/dated initials on the source document or worksheet that supports the causality noted on the AE form, ensures that a medically qualified assessment of causality was done. This initialed document must be retained for the required regulatory time frame.

16.5 Requirements for reporting AEs

16.5.1 SAE reporting

As soon as an investigator becomes aware of an AE that meets the definition of 'serious,' this must be documented on an SAE Report Form or in an electronic database and include the following: (i) all SAEs that occur from the time of informed consent until 30 days after the treatment discontinuation, and (ii) all SAEs attributed to study treatment or procedure occurring more than 30 days after treatment discontinuation.

These SAEs and their follow-up must be reported within 24 hours to the Exelixis Drug Safety and Merck Global Safety:

- Any SAE occurring from the time of consent until treatment initiation if it causes the patient to be excluded from the trial, or if is the result of a protocol-specified intervention, including but not limited to washout or discontinuation of usual therapy, diet, placebo treatment or a procedure
- Any SAE occurring on study regardless of causality from the time of consent until 30 days after treatment discontinuation
- Any SAE attributed to study treatment or procedure occurring more than 30 days after treatment discontinuation

All reportable SAEs must be sent to the following contacts within 24 hours of the PI's knowledge of the event:

- Exelixis: reports must be sent to Exelixis Drug Safety, [contact] or [contact]
- Merck: reports must be sent to Merck Global Safety, [contact]

The PI will perform adequate due diligence with regards to obtaining follow-up information on incomplete reports. All follow-up information must be sent to Exelixis and Merck within 24 hours of the PI's receipt of the new information. Upon request, queries may be issued for follow-up information.

16.5.2 Reporting of pregnancy and lactation

Any pregnancy or lactation exposure that occurs from the time of treatment initiation through 120 days following cessation of treatment, or 30 days following cessation of treatment if the participant initiates new anticancer therapy, whichever is earlier, must be immediately reported by the investigator. All reported pregnancies must be followed to the completion/termination of the pregnancy, which must also be reported when available.

Pregnancy outcomes of spontaneous abortion, missed abortion, benign hydatidiform mole, blighted ovum, fetal death, intrauterine death, miscarriage, stillbirth, or other disabling or life-threatening complication to the mother or newborn must be reported as serious events (Important Medical Events). If the pregnancy continues to term, the outcome (health of infant) must also be reported. Such events

must be reported within 24 hours to Exelixis Drug Safety and Merck Global Safety (see Section 16.4.1 for contact information).

If a male participant impregnates his female partner, the Principal Investigator must be informed immediately and the pregnancy must be reported as well as described above.

16.5.3 Reporting of pembrolizumab overdose

For purposes of this study, an overdose of pembrolizumab is defined as any dose of 1,000 mg or greater (≥ 5 times the indicated dose). No specific information is available on the treatment of overdose of pembrolizumab. In the event of overdose, the participant should be observed closely for signs of toxicity. Appropriate supportive treatment should be provided if clinically indicated.

If an AE is attributed to an overdose of pembrolizumab, it must be reported as an SAE, even if no other seriousness criteria are met.

If an overdose of pembrolizumab is taken without any associated clinical symptoms or abnormal laboratory results, the overdose is reported as a non-serious Event of Clinical Interest (ECI), using the terminology “accidental or intentional overdose without adverse effect.”

All reports of overdose with and without an AE must be reported within 24 hours to Exelixis and Merck (see Section 16.4.1 for contact information).

16.5.4 Events of clinical interest

Selected non-serious and serious AEs are also known as Events of Clinical Interest (ECI) and must be reported within 2 working days to Merck Global Safety (Attn: Worldwide Product Safety; [contact]) and Exelixis Drug Safety ([contact] or [contact]).

Any ECI occurring on study regardless of causality from the time of consent until 30 days after treatment discontinuation must be reported.

ECIs for this trial include:

1. Overdose of pembrolizumab that is not associated with clinical symptoms or abnormal laboratory results (see Section 16.4.3);
2. Elevated AST or ALT $\geq 3X$ ULN and elevated total bilirubin $\geq 2X$ ULN and, at the same time, ALP $< 2X$ ULN.
 - Any ECI occurring from the time of consent until treatment initiation if it causes the patient to be excluded from the trial, or if is the result of a protocol-specified intervention, including but not limited to washout or discontinuation of usual therapy, diet, placebo treatment or a procedure

16.5.5 Regulatory reporting

The Investigator will assess the expectedness of each related AE. The current cabozantinib Reference Safety Information (Appendix K of the most recent approved Investigator Brochure) and the pembrolizumab Investigator’s Brochure will be used as the reference documents for assessing the expectedness of the event with regards to cabozantinib and pembrolizumab, respectively.

- Expedited reporting will be conducted in accordance with FHCRC/Cancer Consortium IRB policies. Specifically, requirements include reporting unanticipated problems involving risks to research participants or others to the FHCRC/Cancer Consortium IRB within 10 calendar days of the investigator's awareness of the problem. AEs that are (1) unexpected, (2) related or possibly related to the research, and (3) suggest that the research presents a greater risk of harm than was previously known or recognized, are among the unanticipated problems subject to these reporting policies. Exelixis and Merck reserve the right to upgrade the Investigator assessment of an SAE.
- Institutions shall promptly provide all information requested by Exelixis and Merck regarding all adverse events occurring during the conduct of the study.
- Exelixis and Merck will provide relevant product safety updates and notifications, as necessary.

Any AE that does not meet expedited reporting criteria may be reported at the time of continuing review.

17.0 STATISTICAL CONSIDERATIONS

17.1 Sample size calculation

The primary objective of this study is to evaluate the ORR in patients with advanced HCC treated with cabozantinib and pembrolizumab. This Phase 2 trial will be based on Simon's optimal two-stage design.

The null ORR is assumed to be 20%, which was the ORR (by RECIST v1.1) observed in the sorafenib-naïve group treated with nivolumab in the CheckMate 040 trial.⁸ Early phase data with lenvatinib and pembrolizumab as first-line treatment showed an ORR of 35% in the expansion phase and an ORR of 42% in the overall patient population (DLT evaluation and expansion phase) using mRECIST criteria.³⁸ Therefore, the null hypothesis that the true ORR is 20% will be tested against a one-sided alternative that the assumed-true ORR with the tested combination is 38% by RECIST v1.1. The target assumed-true ORR of 38% is believed to adequately represent the potential activity of cabozantinib and pembrolizumab.

Using Simon's optimal two-stage design, 13 patients will be accrued in the first stage. If there are 2 or fewer patients with response (CR or PR) (an observed rate of 15% or less), the study will be suspended for lack of sufficient efficacy. Otherwise, 16 additional patients will be accrued for a total of 29 patients. The null hypothesis (of an ORR of 20%) will be rejected if 9 or more patients have a tumor response (CR or PR) out of 29 patients (an observed ORR of at least 31%). This design yields a type I error rate of 0.10 and power of 80% when the true ORR is 38%.

An accrual period of 24 months and follow-up period of 12 months are anticipated. More than 29 patients may be screened and/or enrolled depending on screen fails or dropouts before starting treatment.

17.2 Statistical methods

The primary endpoint is ORR per RECIST v1.1, while secondary endpoints include ORR by iRECIST, ORR and DCR by iRECIST, median PFS, and median OS. Only patients who have been on treatment with both cabozantinib and pembrolizumab concurrently for more than 42 days in the first 3 cycles (i.e. received treatment for two-thirds of the cycle) will be included in the analysis of the primary endpoint. Patients who have received any duration of study treatment will be evaluable for safety.

Binary endpoints will be summarized by percentages and associated confidence intervals. ORR will also be represented by a waterfall plot. The distribution for survival times will be estimated using the method of Kaplan-Meier; associated landmark time percentages and the median value will be based on this. Confidence intervals for median values will use the Brookmeyer-Crowley method. Any toxicity with at least 5% prevalence has at least an 77% chance of being observed among 29 patients.

For the exploratory objectives, archival or fresh tumors from all patients will be analyzed by IHC, the presence of specific immune cell subsets and protein marker expression, as well as the staining pattern and location within tumors will be described. The frequencies of immune cell subset will be obtained from flow cytometry at various timepoints, and cell changes from baseline to post-treatment timepoints will be averaged across patients. The association between immune cell, biomarker expression, gene expression signature, or cytokine level with ORR will be evaluated using Spearman correlation, where $p<0.05$ is considered significant.

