7.3 Duration of therapy

Patients will begin cabozantinib and pembrolizumab concurrently. Patients may continue study therapy until unequivocal disease progression, unacceptable drug-related toxicity, or subject withdrawal. If one drug needs to be permanently discontinued due to toxicity, the other agent may be continued. Interval dosing interruption/delay of either or both agents is allowed for AEs (see Section 9.0).

Treatment beyond progression with cabozantinib and/or pembrolizumab (depending on patient tolerance) will be allowed based on meeting pre-specified criteria and after discussion with the study PI (see Section 12.1).

Patients may be treated up to a maximum of two years from the time of treatment initiation.

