9.4 Dose levels of cabozantinib

Cabozantinib must be started at 40 mg orally once daily and reduced to 20 mg orally once daily (minimum dose) for toxicity. Cabozantinib must be discontinued permanently if the minimal dose is not tolerated. Re-escalation to 40 mg once daily is not recommended, but may be allowed if there is a reason to believe that the patient will tolerate this dose after discussion with the PI.

Table 9.4.1. Dose levels for cabozantinib		
Dose Adjustment Level	Oral Dose	Frequency
0 (starting dose)	40 mg	Once daily
-1	20 mg	Once daily
-2		Discontinue

9.5 Guidance on dose modification of cabozantinib and pembrolizumab for non-immune and immune toxicities

Both non-immune and immune-mediated toxicities may occur on study.

The sections below provide guidance on dose modifications for TRAEs, in addition to management recommendations for cabozantinib-specific toxicities discussed in Section 9.3. However, management

RG1007034

may differ from this guidance based on the clinical judgement of the investigator. In all patients, supportive care should be initiated to manage the AEs in addition to dose modification of study drugs.

For potential irAEs, please refer to the ASCO Clinical Practice Guidelines for Management of Immune-Related Adverse Events in Patients Treated With Immune Checkpoint Inhibitor Therapy.⁵⁸

If dose is interrupted for TRAEs, cabozantinib must be resumed within 4 weeks of last dose, and pembrolizumab must be resumed within 12 weeks of last dose. Resuming drugs beyond these time points must be discussed with the Study PI.

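### The primary ORR set requires more than 42 days on both drugs, so early failures leave the denominator, and the 2/13 and 9/29 rules are not defined for the set that remains

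*Combined protocol and SAP*

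**What the plan says.** Section 17.1 states that "This Phase 2 trial will be based on Simon's optimal two-stage design". Thirteen patients are accrued first, and the study is suspended if 2 or fewer respond. Otherwise 16 more are accrued. At the end, the null hypothesis of a 20% ORR "will be rejected if 9 or more patients have a tumor response (CR or PR) out of 29 patients", which the section also expresses as an observed rate of at least 31%. The stated type I error is 0.10, and the stated power is 80% at a true ORR of 38%. On going beyond 29, it says: "More than 29 patients may be screened and/or enrolled depending on screen fails or dropouts before starting treatment". Section 2.0 describes the same design in terms of eligible, enrolled patients.

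Section 17.2 then defines a narrower set for the primary endpoint: "Only patients who have been on treatment with both cabozantinib and pembrolizumab concurrently for more than 42 days in the first 3 cycles". The next sentence defines the safety set differently: "Patients who have received any duration of study treatment will be evaluable for safety".

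Three other sections bear on who qualifies. Section 11.2 puts the first on-treatment scan at 9 weeks. Section 7.3 says: "If one drug needs to be permanently discontinued due to toxicity, the other agent may be continued". Section 9.5 says that after an interruption for treatment-related events "cabozantinib must be resumed within 4 weeks of last dose, and pembrolizumab must be resumed within 12 weeks of last dose", with later resumption to be discussed with the study PI.

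Nothing in the documents scores excluded patients as non-responders or plans an ORR in all treated patients.

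**The concern.** Membership of the primary set depends on what happens after treatment starts, and what happens is related to the outcome. A patient who dies, progresses clinically or stops either drug for toxicity by day 42 cannot reach more than 42 concurrent days, and leaves before the first scheduled scan. Those patients are treatment failures, and an ORR should count them. Early radiographic progression does not always exclude a patient, because Section 12.1 lets clinically stable patients continue.

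The rule can also remove responders. A patient who continues on one drug, or who has a permitted hold, may respond later and still fail the condition. How concurrent days are counted during a hold, or for a drug infused every 3 weeks, is not stated. The explanatory parenthesis refers to two-thirds of a single cycle, whereas 42 of 63 days is two-thirds of three cycles.

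The decision rules are written for 13 and 29 patients and have no stated form for a smaller set. The plan leaves open whether the stage 1 look uses the 42-day set, whether treated but excluded patients are replaced, and whether the final bar is 9 responders or 31%. The trial is open and single-arm, and Section 18.2 has responses reviewed at least monthly, so these choices could be made with responses known.

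**Working it through.** **Inputs from the documents.** Stage 1: 13 patients, continue with 3 or more responders. Final: 29 patients, reject with 9 or more. Null ORR 0.20, alternative 0.38, one-sided (Section 17.1). Qualifying condition: more than 42 of the first 63 days (Section 17.2).

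**Assumptions.** The documents give no estimate of the share f of treated patients excluded, so 5, 10, 15 and 20% are used. The ORR among excluded patients, q, is set at 0, 10 or 20%. The true all-treated ORR is set at 20%.

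**Step 1: the plan's own figures.** P(reject) = Σ over x = 3 to 13 of Bin(13, x; p) × P[Bin(16; p) ≥ 9 − x]. At p = 0.20 this is 0.0999 and at p = 0.38 it is 0.804. The stated 0.10 and 80% are right, provided all 13 and all 29 patients count.

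**Step 2: will all 29 qualify?** The chance is (1 − f)^29: 0.23, 0.05, 0.01 and 0.002 for f = 5, 10, 15 and 20%.

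**Step 3: expected ORR in the 42-day set.** pe = (0.20 − f·q)/(1 − f). For example, f = 10% and q = 0 gives 0.20/0.90 = 22.2%.

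**Step 4: type I error under three readings.**

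- Reading (a): excluded patients are replaced until 13 and 29 are evaluable. The Step 1 formula is evaluated at pe. Section 17.1 does not provide for this; it is the worst case.
- Reading (b): no replacement, stage 1 needs 3 responders, and the final bar is 9/29 (31%) of the evaluable set. This is the exact sum over the numbers evaluable, m1 ~ Bin(13, 1 − f) and m2 ~ Bin(16, 1 − f), of P[X1 ≥ 3 and (X1 + X2)/(m1 + m2) ≥ 9/29], with X1 and X2 binomial at pe.
- Reading (c): no replacement and the count of 9 kept. This is closest to the text. A patient counts as a responder with probability p(1 − g), where g is the share of responders excluded.

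| | f = 5% | 10% | 15% | 20% |
|---|---|---|---|---|
| Expected ORR, q = 0 | 21.1% | 22.2% | 23.5% | 25.0% |
| Expected ORR, q = 10% | 20.5% | 21.1% | 21.8% | 22.5% |
| (a) type I error, q = 0 | 0.128 | 0.164 | 0.210 | 0.268 |
| (a) type I error, q = 10% | 0.11 | 0.13 | 0.15 | 0.17 |
| (b) type I error, q = 0 | 0.103 | 0.123 | 0.159 | 0.203 |
| (b) type I error, q = 10% | 0.09 | 0.10 | 0.11 | 0.13 |

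At q = 20% the expected ORR stays at 20%; reading (a) gives 0.0999 and reading (b) 0.07–0.08. If stage 1 in (b) is also read as a rate (more than 2/13 of those evaluable), q = 0 gives 0.107, 0.133, 0.177 and 0.234.

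For (c), if all excluded patients are non-responders, the decision is the same as in all treated patients. With g = 5% and 10%, type I error falls to 0.077 and 0.058, and power falls from 0.804 to 0.744 and 0.674.

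**Step 5: one dataset, two answers.** Eight responders among 29 treated is 8/29 = 27.6%, which fails. Exclude 4 non-responders and it is 8/25 = 32.0%, which passes a 31% bar but fails a count of 9.

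**Step 6: permitted holds.** If held days count as off treatment, a 4-week cabozantinib hold within the first three cycles leaves 63 − 28 = 35 days, which does not exceed 42. The patient is excluded whatever the later response.

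**The case against.** The strongest reply is that the text, read closely, does not inflate the type I error. Section 17.1 states the final rule as a count and gives 31% only as its equivalent, and extra enrolment is tied to losses before treatment starts. On that reading, excluding non-responders changes no decision. This stands, and the replacement figures should be read as outside the text. But the plan never says what happens with fewer than 29 evaluable patients, the reported ORR and its confidence interval would still use the selected denominator, and excluding responders would still cost power.

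Only failures in about the first six weeks, and long holds, remove a patient, and eligibility (Child-Pugh A, ECOG 0–1, life expectancy of at least 12 weeks) limits very early failure. The 20% exclusion, zero-response cells are therefore extreme. That also stands, and it is why the range and the milder q values are shown.

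The iRECIST response rate carries no 42-day restriction, and PFS and OS run from registration, so early failures are visible elsewhere. But the iRECIST denominator is not stated, and none of these is the tested endpoint.

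Finally, an all-treated analysis has 80% power only if 38% is the all-treated ORR. If 38% applies only to adequately exposed patients and the rest never respond, power is 0.744 at 5% excluded, 0.674 at 10% and 0.511 at 20%. That is correct. However, Section 17.1 states its power at a true ORR of 38% with 29 accrued patients in the denominator, and for that quantity the stated figures are restored.

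**Conclusion.** The concern holds and should be fixed before the primary analysis. As written, the only planned primary ORR conditions on tolerating both drugs for more than 42 days. It overstates the all-treated ORR whenever excluded patients respond less often than the rest: by 1 to 5 percentage points at a true 20% if 5–20% are excluded and none responds, by 0.5 to 2.5 points if they respond at 10%, and not at all if they respond at 20%.

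The stated type I error and power have no defined denominator, and both can move either way. Under the reading closest to the text there is no type I inflation, but power drops to 0.74–0.67 if 5–10% of responders are excluded. Under a 31% bar without replacement, type I error runs from about 0.07 to 0.20. All these sizes rest on the assumed excluded share and response rate; the two gaps (a post-baseline analysis set, and decision rules not linked to it) do not.

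**What to change.** Replace the 42-day sentence in Section 17.2 with wording such as: *The primary analysis includes all eligible patients who received at least one dose of study treatment. Patients without an evaluable post-baseline scan, for any reason, count as non-responders. The stage 1 and final rules apply to the first 13 and first 29 such patients; treated patients are not replaced.* The word *eligible* keeps it in line with Section 2.0; eligibility should be judged on baseline data only. Applied to this set, 2/13 and 9/29 have type I error 0.0999 and power 0.804 at an all-treated ORR of 38%.

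Keep the 42-day set as a labelled supportive analysis. State how concurrent days are counted during holds and for a drug given every 3 weeks, and correct the parenthesis to two-thirds of the three cycles.

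The cost is one paragraph, with no extra patients or procedures; Section 17.2 already uses the all-treated set for safety. The headline ORR may be lower, and if the team believes 38% applies only to adequately exposed patients, it should acknowledge the lower power shown above.
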